Title of the Study :

A Randomized, Parallel group, Pilot Study on the Effect of using the Portal724-Medication Electronic Medication System (MEMS) Smart Cap with Real-time Clinician Feedback on Medication Adherence Among Patients Infected with Chronic Hepatitis C (HCV) Being Treated with Grazoprevir/Elbasvir

Investigators :

[name], [name] [name].,

Introduction / Rationale of the Study**Hepatitis C and Adherence**

Hepatitis C virus (HCV) infection is a very important health problem worldwide. Majority of the estimated 160 million people infected globally are unaware of their affliction [1]. It is a leading cause of chronic hepatitis, liver cirrhosis and hepatocellular carcinoma. In the United States alone, HCV infection is the most common chronic blood-borne infection, affecting about 3.2 million individuals [2]. It is most prevalent among persons born from 1945-1965, most of whom acquired it in the 1970's and 1980's, since identification of HCV only occurred in 1989 as specific pathogen and blood products screening for the virus was non-existent [4]. Because at least 80% of those who acquire HCV will become chronically infected, it is the number one cause of chronic liver disease and liver cancer in the U.S. [3], and has surpassed HIV in terms of number of deaths [5] and the approximate U.S. economic burden is about \$6.5 billion, inclusive of patients needing liver transplantation [2].

Steps have been taken to decrease this present and future healthcare and economic burden. Shortly after discovery of the virus, blood and blood-derived products started to be screened which led to a dramatic decrease in new incident cases. By 2001, the Needlestick Safety and Prevention Act was passed in the U.S., further decreasing new cases [7]. The CDC has also recommended a one-time screening for persons born between 1945 and 1965, as this segment of the population is at increased risk for HCV infection due to non-screening of blood products before 1989. Despite these measures, the Centers for Diseases Control and Prevention (CDC) estimates there are still about 17,000 new cases occurring yearly [3].

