Electronic assisted compliance is not the sole indicator of MEMS, it is also used in conjunction with answers about demographics, clinical state and symptoms to learn more about the patient characteristics that influence whether a medication regimen is adhered to.

Portal724-MEMS is HIPAA Complaint and ISO27001 Certified. The Electronic Data Capture, the Data Transfer and Data Access are all confidential and Secure in every stage of the Data

Flow Model. The device to be used in this study is a Smart Cap with Pill Dispensing and Integrated Cellular Modem.

Objective

Primary: To determine the effect of the use of Portal724-MEMS Service on medication adherence in the treatment of Hepatitis C patients with grazopravir/elbasvir with or without Ribavirin, defined as compliance to regimen 95% of the time.

Methods

Study design: Open-label, randomized, single center pilot study.

Treatment Arms:

Genotype 1a, treatment naïve or PegIFN/RBV experienced without baseline NS5A polymorphisms with elbasvir/grazoprevir for 12 weeks

Genotype 1a, treatment naïve or PegIFN/RBV experienced with baseline NS5A polymorphisms with elbasvir/grazoprevir/ribavirin for 16 weeks

Genotype 1b, treatment naïve or PegIFN/RBV experienced for 12 weeks

Genotype 1a or 1b, PegIFN/RBV/PI-experienced with elbasvir/grazoprevir/ribavirin for 16 weeks

Genotype 4: treatment naïve with elbasvir/grazoprevir for 12 weeks

Genotype 4: PegIFN/RBV- experienced with elbasvir/grazoprevir/ribavirin for 16 weeks

Proposed number of participants: 40 patients infected with HCV (20 for each group)

Data Collection Time Period: approximately 1 year

Site of Enrollment:

Liver Center at Saint Michael's Medical Center. [name].

In the Liver Center, the main Hepatitis / Infectious Diseases Physician that this study will collaborate with is [name], MD.

Study Patient Population

Treatment-naïve and treatment-experienced genotype 1 and 4 HCV patients with or without compensated cirrhosis will be enrolled in this study.

The inclusion criteria for study are as follows:

1. Male or female 18 years old and above.
2. Be HCV treatment naïve
3. HCV RNA PCR \geq 10,000 IU/L
4. Confirmed infection with Hepatitis C virus (HCV) by HCV serum antibody assay and by HCV Ribonucleic Acid (RNA) Polymerase Chain Reaction (PCR) and Confirmed chronicity with 2 PCR's 6 months apart.
5. Patients with HCV Genotype 1, 4

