- hormonal contraceptive: oral contraceptive pill (estrogen/progestin pill or progestinonly pill), contraceptive skin patch, vaginal contraceptive ring, or subcutaneous contraceptive injection

†Abstinence (relative to heterosexual activity) can be used as the sole method of contraception if it is consistently employed as the subject's preferred and usual lifestyle and if considered acceptable by local regulatory agencies and ERCs/IRBs. Periodic abstinence (e.g., calendar, ovulation, sympto-thermal, post-ovulation methods, etc.) and withdrawal are not acceptable methods of contraception.

0455LH

Enrollment

Upon signing the informed consent, the following data will be gathered prior to start of treatment: demographic data such as age, gender, race/ethnicity, highest educational attainment, employment status, co-morbid conditions as documented in the patient's records, current medications, vital signs (blood pressure, heart rate, respiratory rate, temperature), CBC with differential count, complete metabolic panel, 12-Lead Electrocardiogram (EKG), Cardiac stress test results if applicable, echocardiogram results if applicable, , BMI, baseline HCV RNA PCR

viral load, HCV genotype, baseline HCV resistance testing (if indicated), results of the Fibroscan® test or liver biopsy.

Once the informed consent is signed and the patient is deemed eligible for treatment, the patient will be randomized to either ARM 1 or ARM 2 in a 1:1 ratio. ARM 1 will be prescribed elbasvirir/grazoprevir with/or without ribavirin for 12 or 16 weeks 1 tablet daily with MEMS Smart Cap with real-time monitoring. Arm 2: elbasvir/grazoprevir with/or without ribavirin for 12 or 16 weeks 1 tablet daily MEMS Smart Cap without real-time monitoring.

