For Group 1, the cap of the study drug bottle will be replaced with the Portal724- MEMS Smart Cap. A cellular phone per patient will also be provided. The Smart Cap in this study is to be outfitted to send messages to a website to which only the investigators and the research assistants have access to monitor medication adherence. Patients are to be instructed to open their study drug bottles in areas where there is at least 1 cellular signal bar. Patients will also be instructed to take their medications at specific agreed upon times. Once the agreed upon times are set, these will be programmed into the Smart Caps through a software program. The Smart Caps are encoded to not only record each pill bottle opening, it also will transmit an alert to the aforementioned website when the bottle is not opened within 2 hours of the agreed upon time. This alert is then seen by the Investigator or the Research assistant through a computer or their smartphone. The Investigator or Research Assistant in turn calls the cellular phone provided to the patient to remind the participant to take their medication, thus providing real-time feedback. Group 2 (the control group) will be provided MEMS Smart Cap to record study drug bottle opening, but without real-time feedback and will be managed as per the standard of care at the Liver Center SMMC.

Patients from both groups will be seen in the Liver Center at Day 1, weeks 2, 4, 8 and 12 from start of treatment. They will be seen by Liver Center Physician together with the Investigator and Research Assistant at each visit. They will also be counseled about the importance of medication adherence at every visit by the Liver Center physician. At each visit, patients are instructed to bring with them all of their anti-HCV study drug bottles for pill counting to be done by the Investigator and Research Assistant. Patients in ARM 1 will also get feedback about their medication compliance using the Smart Caps per visit.

After completion of treatment as determined by the Liver Center Physician, patients from both groups are to follow-up at week 4 and week 12 post-treatment. At that time, an HCV RNA PCR viral load will be obtained to determine if patient has an undetectable viral load, or Sustained Virologic Response (SVR). SVR is the marker for a functional cure of HCV, or treatment success. Non-SVR would mean treatment failure.

Study Procedures	Pre-Treatment						Treatment Assessments		Post Tx	Post tx

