	Screening (Day 35 to -1)	Baseline (Day 0)	WK2	Wk4	Wk8	Wk12/16	Wk 4	Wk 12		
	Informed Consent w/ Med Hist inc HIV status	x								
Complete PE inc. Vital Signs	x	x								
Symptom Directed PE inc. Vital Signs			x	X	X	X	x	x		
12-lead ECG	x									
Chemistry(Comprehensive Metabolic Panel)	x	x	x	x	x	x	x	x		
Hematology	x	x	x	x	x	x	x	x		
Virology(HCV)	x	x	x	x	x	x	x	x		
AEs		X	X	X	X	X	X	X		
Con Meds	X	X	X	X	X	X	X			
MEMS download		x	x	x	x	x				

Data Collection

At each visit, the following data are to be collected: HCV RNA PCR viral load, CBC, complete metabolic profile, number of pills missed. For both groups, Number of times pill bottles were opened will also be collected.

Primary outcome measures:

Primary endpoint in the study is the effect of the use of Portal724-MEMS Service on medication adherence, defined as compliance to regimen $\geq 95\%$ of the time.

Secondary outcome measures:

The secondary endpoints for the study include the effect of the use of Portal724-MEMS Service on SVR, factors that affect medication adherence, such as race/ethnicity, age, educational attainment. Additionally, the feasibility of using MEMS adherence technology in an inner city urban population will be evaluated.

Statistical Analysis

This is a pilot study intended to generate initial data on the use of MEMS technology in an inner city population to assess its feasibility and impact on treatment outcomes in HCV infected patients. Wilcoxon signed-rank test will be used to compare Groups 1 and 2 in terms of achieving adherence 95%.

SVR between the groups will also be analyzed in the same manner. A descriptive analysis will be done outlining patients' profiles. Fischer's exact test will be used to compare baseline characteristics between Groups 1 and 2. Alpha level for all statistical analysis will be set at 0.05.

Toxicity management

Grazoprevir/elbasvir

The following side effects have been reported when MK-5172 in doses ranging from 25 mg to 800 mg or placebo (a tablet that looks the same as the MK-5172 but has no active ingredient) was given for up to 12 continuous weeks to 389 HCV-infected men and women at the same time as other drugs commonly given to HCV patients (pegylated interferon and ribavirin). These side effects were considered to be related to the treatment.

- Decrease in the blood cells that carry oxygen
- Decrease in blood cells that fight infection
- Stomach pain
- Diarrhea
- Upset stomach
- Dry mouth
- Nausea
- Vomiting
- Weakness
- Chills
- Fatigue

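### A paired test (Wilcoxon signed-rank) is named for two unpaired groups with yes/no outcomes, so the primary p-value can depend on an arbitrary pairing of patients

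*Combined protocol and SAP*

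**What the plan says.** The title describes "A Randomized, Parallel group, Pilot Study". Under Enrollment, "the patient will be randomized to either ARM 1 or ARM 2 in a 1:1 ratio", and the Methods section proposes 40 participants, 20 per group. No matching, crossover or within-patient comparison is described.

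Under Primary outcome measures: "Primary endpoint in the study is the effect of the use of Portal724-MEMS Service on medication adherence, defined as compliance to regimen" at least 95% of the time. SVR is also a two-state outcome; the Enrollment section says "Non-SVR would mean treatment failure".

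The Statistical Analysis text appears twice, once after the outcome measures and once after Confidentiality. Both copies say "Wilcoxon signed-rank test will be used to compare Groups 1 and 2 in terms of achieving adherence" at the 95% threshold, then "SVR between the groups will also be analyzed in the same manner". Both also say "Fischer's exact test will be used to compare baseline characteristics between Groups 1 and 2". The first copy sets alpha at 0.05 for all analyses; sidedness is not stated. No other between-group test is named for the primary endpoint or SVR.

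**The concern.** The signed-rank test ranks the differences within pairs. Here the two groups hold different people and nothing links a patient in one arm to a patient in the other. To run the test, an analyst must line the arms up in some order, and the plan gives no rule for this.

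The outcomes make it worse. With a yes/no outcome every non-zero difference is +1 or -1, so there is nothing to rank and the test becomes a sign test on the discordant pairs. How many pairs are discordant depends on who was put next to whom. If the arms finish with unequal evaluable numbers, some patients have no partner and drop out of the test. That is foreseeable, because the Toxicity management section requires withdrawal after certain reactions.

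At stake is the only inferential analysis named for the primary endpoint and for SVR. Meanwhile Fisher's exact test, which suits two independent groups and a yes/no outcome, is assigned to baseline characteristics, several of which (age, BMI, viral load) are continuous.

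**Working it through.** The documents give no expected adherence rate, effect size or power, so there is no stated figure to reproduce.

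**Inputs.** From the documents: 20 patients per arm, two independent groups, binary outcomes, alpha 0.05. Assumed: two-sided testing, and the adherent counts x1 and x2 below.

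**Method.** Pair the 20 patients of one arm with the 20 of the other. Let k be the number of pairs in which both are adherent. The discordant pairs are b = x1 - k and c = x2 - k. The difference b - c = x1 - x2 is fixed by the data; the total b + c = x1 + x2 - 2k depends on the pairing.

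- Exact signed-rank p (all absolute differences equal 1): the two-sided binomial probability for b out of b + c with probability 0.5.
- Asymptotic signed-rank p: z = (b - c)/√(b + c), no continuity correction.
- Share of random pairings giving each split: hypergeometric.

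**Worked case, 18/20 versus 12/20.** The 2 non-adherent patients in Group 1 each face one of 8 non-adherent or 12 adherent patients in Group 2. There are C(20,2) = 190 equally likely ways.

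- Both face non-adherent patients: 28/190 = 14.7%. Split 6 v 0. Exact p = 2 × (1/2)^6 = 0.031; z = 6/√6 = 2.45, p = 0.014.
- One does: 8 × 12/190 = 50.5%. Split 7 v 1. Exact p = 2 × 9/256 = 0.070; z = 6/√8 = 2.12, p = 0.034.
- Neither does: 66/190 = 34.7%. Split 8 v 2. Exact p = 2 × 56/1024 = 0.109; z = 6/√10 = 1.90, p = 0.058.

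**Results for three tables**

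| Adherent | Fisher p | Exact signed-rank p | Pairings with exact p < 0.05 | Asymptotic signed-rank p | Pairings with asymptotic p < 0.05 |
|---|---|---|---|---|---|
| 18/20 v 12/20 | 0.065 | 0.031, 0.070 or 0.109 | 14.7% | 0.014, 0.034 or 0.058 | 65% |
| 19/20 v 13/20 | 0.044 | 0.031 or 0.070 | 35% | 0.014 or 0.034 | 100% |
| 20/20 v 15/20 | 0.047 | 0.0625 | 0% | 0.025 | 100% |

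The plan does not say which version would be used, and that choice alone moves the third table across 0.05.

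**Error rates (enumerated over all tables, 20 per arm).** For common true rates from 0.5 to 0.9, with random pairing, the type I error is 0.3% to 2.3% for the exact version and 4.0% to 4.7% for the asymptotic one. If the most favourable pairing were picked, the asymptotic version would reject a true null 6% (rate 0.9) to 27% (rate 0.5) of the time. At assumed true rates of 0.90 versus 0.60, power is 49% for Fisher, 43% for exact signed-rank and 57% for asymptotic signed-rank with random pairing.

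**The case against.** Several points on the other side are fair.

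- **The p-value does not always move.** When one arm is at 100%, every pairing gives the same p. Near the ceiling, where SVR may lie since the Introduction cites cure rates above 90% for newer oral combinations, pairing matters little: at 19/20 versus 18/20 the exact p is 1.0 under every pairing. This stands, so the right word is that the result can change.
- **Type I error is not inflated if the pairing is random.** This also stands. The harm is a non-unique answer and freedom to choose a pairing.
- **The signed-rank test is not always the less favourable one.** The asymptotic version often gives smaller p-values than Fisher, as the table shows. That adds another unspecified choice.
- **Unequal arms do not stop all computation.** The test could be run on a subset; it just cannot use every patient.
- **It may be a slip for rank-sum.** Possibly, but signed-rank is written in both sections. An analyst would have to follow it or replace the primary test without a plan, perhaps after seeing the data.
- **It is a pilot.** True, and no power claim is undermined. But the plan sets an alpha level, intends publication, and will use the results to decide on a larger study.

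None of these supplies pairs.

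**Conclusion.** The concern holds and should be corrected before any data are analysed. The named test does not fit the design, and for many plausible tables it yields several p-values from the same data, some on each side of 0.05. The mismatch itself follows from the documents alone. The sizes rest on assumed counts at 20 per arm, two-sided testing and full follow-up. They vary with the version of the test and vanish when an arm is at 100%. The demonstrated fault is an undefined primary result, not a raised false-positive rate under random pairing.

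**What to change.** In both Statistical Analysis sections, replace the signed-rank test with a two-sided Fisher's exact test, for adherence of at least 95% and for SVR. Report the difference in proportions with a 95% confidence interval for each. Keep the two copies identical, including the alpha level and sidedness.

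Two secondary changes are worth making at the same time, though the case does not rest on them:

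- Add a Wilcoxon rank-sum (Mann-Whitney) test on each patient's percent adherence as a supportive analysis. Under an assumed beta-binomial model with 84 doses (12 weeks × 7) and 20 per arm, mean adherence of 88% versus 95% (precision 12) gives about 84% power, against 57% for Fisher at the 95% cut. At 92% versus 95% the figures are about 31% and 14%. These figures ignore the 16-week regimens.
- Report baseline characteristics descriptively by arm, without tests.

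The cost is a few sentences of wording, with no extra data or patients, since pills missed and bottle openings are already collected in both groups. The plan should also say which of those two measures defines percent adherence; the 95% cut needs that as well.

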Treatment of HCV has been the main focus of clinical research since vaccine research has proved to be difficult, as well as the necessity of treating undiagnosed individuals. Among the 7 major HCV genotypes, genotype 1 is by far the most prevalent in Europe and in the United States. It has historically been the most difficult type to treat. Prior to 2011, the standard treatment for HCV was a combination of once-weekly injectable Pegylated Interferon with daily

oral Ribavirin to be taken for 48 weeks. The cure rate, measured as sustained virologic response (SVR) for this regimen is a dismal 40-50% [6]. Adherence to the treatment was difficult for many patients due to the length of therapy and the associated side effects of both interferon and ribavirin. The addition of new directly acting agents (DAA), Boceprevir and Telaprevir in 2011, revolutionized HCV treatment, increasing cure rates up to 75%. However, adherence continued to plague therapy because of side effects and thrice-daily dosing.

In 2013, 2 new DAA's were FDA-approved, ushering in the interferon-free era of HCV therapy. Sofosbuvir and Simprevir are once daily oral agents with much fewer side effects than any previous anti-HCV medication. Ledipasvir, another oral DAA, has been approved by the FDA in October 2014, to be given as a single tablet regimen together with Sofosbuvir. The length of treatment has also decreased, from 48 weeks to 12-24 weeks, and clinical trials of the combination of these drugs showed cure rates above 90%, with increased tolerability and safety [8]. Other DAA's since then have been approved by the FDA such as the combinations of ombitasvir/paritaprevir/ritonavir (Viekira Pak) and Grazopravir/Elbasvir (**Zepatier**).

are in clinical trials or under FDA review, increasing the chances that more patients can be cured from HCV infection.

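### SVR is compared between arms only by a 0.05-level paired test on two independent groups of 20; it needs a between-arm difference with a 95% interval, because a p-value alone says little at this size

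*Combined protocol and SAP*

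**What the plan says.** SVR is a secondary endpoint: the outcome section lists the effect of the monitoring service on it. The Statistical Analysis section appears twice, once after the outcome measures and again after Confidentiality. Both versions give the same rule for SVR: "SVR between the groups will also be analyzed in the same manner". The manner referred to is set one sentence earlier: "Wilcoxon signed-rank test will be used to compare Groups 1 and 2 in terms of achieving adherence 95" per cent. The first version adds "Alpha level for all statistical analysis will be set at 0.05"; the second omits that sentence. Fisher's exact test is named for a different purpose only: "Fischer's exact test will be used to compare baseline characteristics between Groups 1 and 2".

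The Methods give the size, "Proposed number of participants: 40 patients infected with HCV (20 for each group"), and the Enrollment section gives the allocation, "the patient will be randomized to either ARM 1 or ARM 2 in a 1:1 ratio". For SVR the plan states no expected rate, detectable difference, power, effect estimate or confidence interval. The only cure rate for interferon-free treatment is in the Introduction, where "clinical trials of the combination of these drugs showed cure rates above 90" per cent. That sentence follows the account of sofosbuvir, simeprevir and ledipasvir. Grazoprevir/elbasvir is mentioned afterwards, without a rate.

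**The concern.** There are two difficulties, and curing the first does not cure the second.

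- **The test does not fit the design.** A signed-rank test works on within-pair differences. Patients here are randomised individually to two arms and nothing links a patient in one arm to a patient in the other. Any pairing would be arbitrary, and unless one arm has a perfect record the p-value can change with the pairing chosen.
- **A p-value is the only between-arm SVR result planned.** When most patients in both arms are expected to be cured, very few failures carry the comparison. Twenty per arm will then nearly always give a non-significant result, whether or not real-time feedback helps.

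At stake is what the trial can say about SVR. A bare non-significant p-value does not show which differences remain possible, so it invites the reading that feedback has no effect on cure. The investigators plan to present and publish the results, and envisage a larger programme if the technology proves workable and useful. Planning that work needs counts and an interval.

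**Working it through.** The plan states no power or detectable difference for SVR, so there is no figure of its own to reproduce.

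**Inputs**
- From the documents: 20 per arm, 1:1 allocation, alpha 0.05.
- Assumed: two-sided testing (sidedness is not stated); all 20 per arm evaluable (no dropout rate is given); control SVR of 90%, then 85%, 80% and 95% to show sensitivity.
- Arm 1 is set at 20/20, the most favourable case for finding a benefit.

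**Step 1. Control failures needed for p < 0.05.** Let f be the number of failures in Arm 2.
- Fisher, two-sided: p = 2 × C(20,f) / C(40,f).
- Uncorrected chi-square: X² = 40 × (20f)² / [20 × 20 × (40 − f) × f]. At f = 4 this is 256,000 / 57,600 = 4.44, p = 0.035. The rank-sum normal approximation gives p = 0.037 (0.040 with continuity correction).
- Signed-rank on arbitrary pairs: with Arm 1 perfect there are f non-zero differences, all in one direction and all tied. Exact p = 2 × 0.5^f. Normal approximation: z = √f.

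| f | Fisher | Rank-sum, no correction | Signed-rank, exact | Signed-rank, normal |
|---|---|---|---|---|
| 2 | 0.487 | 0.152 | 0.500 | 0.157 |
| 3 | 0.231 | 0.075 | 0.250 | 0.083 |
| 4 | 0.106 | 0.037 | 0.125 | 0.0455 |
| 5 | 0.047 | 0.018 | 0.0625 | 0.025 |
| 6 | 0.020 | 0.009 | 0.031 | 0.014 |

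The thresholds are therefore 4 failures (rank-sum, uncorrected chi-square, signed-rank normal approximation), 5 (Fisher; also signed-rank with continuity correction, p = 0.037) and 6 (exact signed-rank).

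**Step 2. Chance of reaching each threshold.** With Arm 1 at 20/20 this is P(X ≥ k), where X is binomial (20, 1 − control SVR).

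| Control SVR | k = 4 | k = 5 (Fisher) | k = 6 |
|---|---|---|---|
| 95% | 1.6% | 0.3% | 0.03% |
| 90% | 13.3% | 4.3% | 1.1% |
| 85% | 35.2% | 17.0% | 6.7% |
| 80% | 58.9% | 37.0% | 19.6% |

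At 90% control SVR the expected number of control failures is 20 × 0.10 = 2, well short of any threshold. With Arm 1 still at 100%, 80% power by Fisher would need a control SVR of about 69%.

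**Step 3. A less extreme Arm 1.** Summing over all 21 × 21 outcomes for true rates of 95% v 90%, power is 1.7% by Fisher and 5.4% by uncorrected chi-square or rank-sum.

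**Step 4. What an interval would show.** Newcombe's interval combines the two Wilson limits (l₁, u₁) and (l₂, u₂):

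d − √[(p₁ − l₁)² + (u₂ − p₂)²] to d + √[(u₁ − p₁)² + (p₂ − l₂)²].

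Wilson 95% limits are 0.699 to 0.972 for 18/20 and 0.764 to 0.991 for 19/20.
- 18/20 v 18/20: d = 0; half-width √[(0.900 − 0.699)² + (0.972 − 0.900)²] = √(0.0404 + 0.0052) = 0.214, so −21 to +21 points.
- 19/20 v 18/20: d = +5 points; lower 0.05 − √[(0.186)² + (0.072)²] = −0.150; upper 0.05 + √[(0.041)² + (0.201)²] = 0.255, so −15 to +26 points.

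**The case against.** The strongest reply is that this is a 40-patient pilot with SVR as a secondary endpoint. It claims no power for SVR, and low power there is expected and is not a design error. That stands: if the point were only that power is low, it would fail. It rests instead on the choice of a paired test and the absence of any estimate. Pilot status supports reporting an estimate.

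Four stronger readings are tempting, and the documents do not support them.
- **That the SVR test cannot succeed.** The chance is small but not zero, and it depends on the test. The 4% is Fisher's figure, and the plan assigns Fisher only to baseline characteristics. Rank-sum, the unpaired relative of the named test, gives about 13% at 90% control SVR.
- **That 90% is the protocol's expected rate here.** It is background from trials of other combinations. This trial recruits an inner-city population, admits compensated cirrhosis and lists protease-inhibitor-experienced strata, so control SVR could be lower, and Step 2 shows that the result is sensitive to it.
- **That a null result would be reported as no impact.** No passage says so. It is a risk of misreading.
- **That the SVR p-value must go, or the pilot's stated aim be reworded.** That is preference. A p-value from a suitable test, set beside an interval, does no harm.

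**Conclusion.** The point holds in this form. The only planned between-arm SVR analysis is a 0.05-level test that does not suit independent arms, with no estimate or interval. Changing to an unpaired test repairs the mismatch but leaves little information in the p-value. With Arm 1 curing everyone, the chance of significance at 90% control SVR is about 4% by Fisher and between 1% and 13% across tests. Because the background rate is quoted as above 90%, these figures are upper limits for each test at that rate: at 95% they fall below 2%. At 85% the chance is 17% by Fisher and 35% at the four-failure threshold; at 80% it is 37% and 59%. So the conclusion is strong near 90% and weakens if control patients do clearly worse.

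All these figures assume two-sided testing and 20 evaluable patients per arm. The case for an interval does not depend on the assumed control rate, since 18/20 in both arms would still leave about 21 points in either direction open.

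**What to change.** In both copies of the Statistical Analysis section, replace the SVR sentence with text to this effect:

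- The main SVR result is n/N per arm and the between-arm difference with a 95% Newcombe (or exact unconditional) interval, labelled descriptive.
- A non-significant or near-zero difference will not be interpreted as no effect on SVR.
- If a p-value is kept, it comes from an unpaired test such as Fisher's exact, named in advance with its sidedness, and is shown beside the interval.

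The cost is a few sentences and an interval that will look wide. No extra patients, visits or data are needed.
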